
Power and sample size considerations. For Aim 1, to reach a target of 'excellent' usability (mean SUS score >85), we expect 1-2 iterative revision cycles of 8-15 family members and 8-10 clinicians—a sample similar in size to that needed to reach thematic saturation in qualitative analysis (e.g., the 30 patient-level cases (total n=90) we expect will allow us to recognize theme saturation in Aim 4). The effect of interest for Aims 2 and 3 is essentially the T1 - T2 difference between the intervention and usual care groups. Aim 2 focuses on the overall difference and the difference within Black and White patients separately, while Aim 3 focuses on the difference within Black families compared to White families. Therefore, we base our sample size calculations on the mean difference score using tests for two means in a cluster randomized design. The sample size requirements are greatest for Aim 3; as discussed by Leon and Heo (2009), the needed sample size for the family race by intervention group interaction is 4 times that needed for the overall test. Based on preliminary studies, the standard deviation of the change in NEST score is estimated as 12 units and a reasonable range of intraclass correlation coefficients is 0.01 to 0.1. For all calculations, the type I error is 5% and power is 80%. With a sample size of 160 families (4 per each of 40 physicians. 20 per treatment arm), we will be able to detect differences of 4.0 to 5.0 NEST units for Hypothesis 2a in the overall test, 5.4 to 6.1 for Black or White patients separately, and 7.6 to 8.0 units for Hypothesis 3a. For Aim 4, we expect that up to 25 cases comprised of family members will be sufficient to reach informational redundancy—the point at which no new themes emerge.

Ancillary study: Needs and triggers: improving intensive care unit-based palliative care deliveryStatistical methods:

Aim 1: The primary goal of the cohort study (Aim 1) is to derive 3-5 clinically rational palliative care need typologies, or subgroups with a phenotypic homogeneity of need severity and type, to inform Aim 2's derivation of a care delivery model. These analyses will be conducted within the framework of latent class analysis (LCA), a statistical methodology that uses contingency table analyses to discern response patterns across a series of categorical variables. LCA will be applied to the dichotomized (high vs. low need) NEST item scores to identify latent (i.e., unobservable) subgroups of need classes within family members at T1 via maximum likelihood estimation (SAS PROC LCA). Study investigators will iteratively develop more fully formed needs typologies resulting from these analyses in a series of face-to-face investigator meetings using a decision-rule process. We will provisionally classify need typologies as 'simpler' (ICU team can address) or 'complex' (specialist care advised).

Exploratory hypotheses: Hypothesis 1aexplores the potential value of a novel intervention target—'unmet needs,' defined as a NEST summary score at T2 that is greater than T1 for those completing both interviews. This hypothesis will be confirmed if the unmet needs coefficient is statistically significant after regressing PHQ-9 scores at T4. Hypothesis 1bwill tested via a multivariable regression model with NEST summary score as the outcome and trigger status (present / absent) as the coefficient of interest, adjusted for sociodemographic and clinical variables. We anticipate < 10% missing data between T1 and T2.

Aim 2: This Aim's primary goal is to develop a provisional collaborative model of ICU-based palliative care using a mixed methods approach in which qualitative focus group data from family members, self-reported skills confidence data from clinicians, and expert guidelines will be integrated with Aim 1's need typologies. Step 1: validate needs typologies. 3 focus group interviews with family members purposively sampled from each of Aim 1's needs typologies subgroups will be conducted to validate the needs typologies in participants' own voices, verify the complexity of needs, and allow us to look beyond socioemographic variables for other common factors shared by subgroup members. Transcripts will be

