General considerations: The primary analyses will be conducted on an intention-to-treat basis; clinicians and patients will be analyzed in the group to which they were randomized, regardless of clinician intervention adherence, using all available data. The main conclusions drawn from this trial will be based on the pre-specified hypotheses outlined below and will be tested with two-sided p-values at the standard 0.05 level. For all study outcomes, we will interpret differences between groups over time with reference to prior literature regarding clinically meaningful changes. Results from exploratory analyses will be interpreted with appropriate consideration for their exploratory nature. Statistical analyses will be performed using the latest release SAS for Windows (Cary, NC) and R/Rstudio.

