Approach to statistical models: The goal of the primary hypothesis (2a) is to determine the efficacy of the ICUconnect intervention versus usual care on reduction in unmet needs from T1 to T2. Additionally, we are interested the intervention effect within Black families and White families separately. Unmet needs will be assessed at T1 and T2 with the total NEST score, a continuous, normally distributed measure. Because each family member is surveyed at multiple time points and the same ICU physician sees several patients, outcome variable measurements will not be independent. We, therefore, plan to use hierarchical linear models as our primary analytic strategy because they appropriately account for the multiple types of correlation inherent in our study design.45 The hierarchical linear model will have the following form: Yijk= b0+ b1(T2) + b2(T2*intk) + b3(racek)+ b4(servicetimek) + b5(ICUtypek)+ bik+ ck+ eijk, where Yijkis the total NEST score for family iat time jand physiciank. In this model, T2and intare indicator variables for the post-treatment and intervention group, respectively. Additionally, we include indicators for the randomization stratification variables. The multiple levels of correlation are captured via the physician-level random effect, ck, and the family-level random effect, bjk. Both random effects and the residual error (eijk) are assumed to be independent and normally distributed. PROC MIXED in SAS (SAS Inc., Cary, NC) will be used to fit the hierarchical linear models and test the primary hypothesis (2a). Specifically, if b2is negative and significantly different than zero, this provides evidence families in the intervention group have reduced unmet needs as compared to usual care group families. The secondary outcome, quality of patient-centered care, is also a continuous measure assessed at T1 and T2. A similar hierarchical linear model will be used to test Hypothesis 2b; in this model, if b2is positive and significantly different than zero, this provides evidence families in the intervention group have improved quality of patient-centered care as compared to usual care group families. Both analyses for Hypotheses 2a and 2b will be repeated within Black and White patients separately, with the goal to ensure that the intervention is effective in both subgroups (as an overall treatment effect can sometimes mask important heterogeneity). Aim 3 addresses relative differences in the intervention effect on reducing disparities.

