Aim 3 Analyses: A hierarchical linear model will again be the primary modeling strategy for the Aim 3 analyses. For this Aim, however, the model will include patient-race interaction terms and will have the following form: Yijk= b0+ b1(Blacki) + b2(T2) + b3(T2*Blacki) + b4(T2*intk) + b5(T2*Blacki*intk) + b6 (racek)+ b7(servicetimek) + b8(ICUtypek)+ bik+ ck+ eijk, where Yijkis the NEST score for family iat time jand physician k. In this model, Blackiis the indicator variable for whether a patient is Black (value of 1) or White (value of 0). Racial disparities in unmet needs at baseline are represented by the estimated value of b1. That is, the estimated baseline mean for White families is b0 and the estimated baseline mean for Black families is b0 + b1, so if the estimate of b1is positive, this indicates that prior to the intervention, Black patients have more unmet needs than White patients. Post-treatment, the Black-white mean difference among usual care group families is BWuc = (b0 + b1 + b2 + b3) - (b0 + b2), and among intervention group families is BWint = (b0 + b1 + b2 + b3 + b4 + b5) - (b0 + b2 + b4). Hypothesis 3a will be tested by the difference between BWint and BWuc, indicating that racial disparities unmet needs are reduced in the intervention group as compared to the control group. The estimated difference, p-value, and 95% confidence intervals will be calculated via estimate statements in PROC MIXED. Additionally, estimated values and confidence intervals will be calculated for BWint as compared to b1 to quantify the magnitude of reduction from baseline. A similar hierarchical linear model will be used to examine the reduction in racial disparities of quality of patient-centered care and test Hypothesis 3b.

Missing Data: The survey data may contain missing values in any of the clinician-level and patient-level variables due to drop-out, death, or item non-response. Our primary analysis technique, hierarchical models, allow for unbalanced or incomplete data and will be fit with maximum-likelihood methods to preserve the missing at random assumption. Additionally, we will thoroughly explore reasons for dropout, and depending upon the type and scope of missing data, variables may be multiply imputed as recommended by guidelines.46Note that if needed, we will utilize imputation methods that account for the multiple levels of correlation inherent in the clustered data structure.

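### On its own stated inputs the power statement's 160 families do not give 80% power for any of its three ranges, and 160 is not reconciled with the 240 to be enrolled

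*Protocol*

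**What the plan says.** The paragraph on power and sample size (protocol, Data Analysis & Statistical Considerations) names its method: "we base our sample size calculations on the mean difference score using tests for two means in a cluster randomized design". It takes an SD of change in NEST of 12, an ICC of 0.01 to 0.1, 5% type I error and 80% power. The Aim 2 general considerations add that hypotheses "will be tested with two-sided p-values at the standard 0.05 level".

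The result is given as "With a sample size of 160 families (4 per each of 40 physicians. 20 per treatment arm), we will be able to detect differences". The overall and one-race figures read "differences of 4.0 to 5.0 NEST units for Hypothesis 2a in the overall test, 5.4 to 6.1 for Black or White patients separately". The disparity hypothesis gets its own range, "7.6 to 8.0 units for Hypothesis 3a". For the interaction the paragraph relies on a rule that "the needed sample size for the family race by intervention group interaction is 4 times that needed for the overall test".

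The trial size appears in four places:

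| Place in protocol | RCT size | Clinicians |
|---|---|---|
| Research Abstract | 160 family members (80 White, 80 Black) | 60 (RCT and ancillary study together) |
| Power paragraph | 160 families | 40 |
| Design & Procedures, Aims 2 and 3 | 240 enrolled dyads | at most 60 |
| Subject Recruitment and Compensation | about 320 consented, 240 enrolled | 30–60 |

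The recruitment section attributes its numbers to statistical power. The SAP gives no sample size.

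**The concern.** Every input needed to check the three ranges is printed, and the ranges do not follow from those inputs. The paragraph covers the primary hypothesis, the two within-race tests and the disparity hypothesis, which it says has the largest sample size requirement. If true power for the interaction is about a half, a reader who trusts the stated 80% would take a null result on disparities as more informative than it is.

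A reader also cannot tell whether the trial is sized at 160 or 240, or to which number the detectable differences belong. The protocol sets no target NEST difference. The error therefore lies in the power statement, and no shortfall against a design target is claimed.

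**Working it through.** **Inputs.** SD of change 12, ICC 0.01 and 0.1, 80% power, N = 160, K = 40 physicians, m = 4 families each, equal arms (power paragraph). Two-sided 5% (Aim 2 general considerations). 80 families per race (Research Abstract). Assumption: each physician's families split evenly by race, so m = 2 within one race.

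**Formula.** SE = 12 × √(4 × (1 + (m − 1) × ICC) / N). The detectable difference comes from the noncentral t with families − 2 df. The normal approximation, 2.8016 × SE, is in brackets.

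**Overall, N = 160, m = 4**
- ICC 0.01: SE = 12 × √(4 × 1.03/160) = 1.926, giving 5.43 [5.39].
- ICC 0.1: SE = 12 × √(4 × 1.30/160) = 2.163, giving 6.10 [6.06].
- ICC 0: SE = 1.897, giving 5.35 [5.32].

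**One race, N = 80, m = 2**
- ICC 0.01: SE = 12 × √(4 × 1.01/80) = 2.697, giving 7.65 [7.55].
- ICC 0.1: SE = 12 × √(4 × 1.10/80) = 2.814, giving 7.98 [7.88].
- ICC 0: 7.61 [7.52].

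**Interaction.** The fourfold rule does not say how clustering enters, so three readings were tried.
- N/4 = 40 families, one per physician: SE = 12 × √(4/40) = 3.795, giving 10.91 [10.63].
- Twice the overall figure: 10.86 and 12.20.
- Within-physician contrast, SE = 12 × √(16 × (1 − ICC)/160): 10.64 and 10.15. Here a higher ICC lowers the figure, but 8.0 would need an ICC of about 0.43.

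**Against the printed values** (lower value with ICC 0.01, upper with ICC 0.1):

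| Comparison | Printed | Recomputed | Power at printed values |
|---|---|---|---|
| Overall | 4.0–5.0 | 5.43–6.10 | 54.2% / 63.2% |
| One race | 5.4–6.1 | 7.65–7.98 | 50.7% / 57.2% |
| Interaction, N/4 | 7.6–8.0 | 10.91 | 49.7% / 53.8% |
| Interaction, twice overall | 7.6–8.0 | 10.86–12.20 | 50.1% / 45.1% |
| Interaction, within physician | 7.6–8.0 | 10.15–10.64 | 51.6% / 59.8% |

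Pairing 5.0 with the favourable ICC of 0.01 still gives only 73% power overall.

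**Where the printed figures might come from.** The recomputed overall range is the one printed for a single race, and the recomputed one-race range is the one printed for the interaction. All three printed ranges are recovered at 320 families, 8 for each of 40 physicians: 3.99–5.03 overall (38 df; 3.90–4.92 with 318 df), 5.43–6.10 within one race, and 7.65–7.98 by the N/4 reading. That 320 was the input is an inference. The protocol uses 320 only as the number to be consented.

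**Does 240 rescue the ranges?** This assumes 120 per race, an equal race mix per physician and the N/4 reading:

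| Physicians | Overall | One race | Interaction |
|---|---|---|---|
| 60 | 4.42–4.97 | 6.22–6.49 | 8.83 |
| 40 | 4.47–5.34 | 6.25–6.78 | 8.85–9.05 |
| 30 | 4.51–5.68 | 6.28–7.06 | 8.87–9.26 |

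At 240 families, 4.0 is not reached even with ICC 0 (4.36). Only the 5.0 is met, and at ICC 0.1 it needs close to the maximum of 60 physicians. Over 30 to 60 physicians, power is 70–72% for 4.0 (ICC 0.01) and 69–81% for 5.0 (ICC 0.1).

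**160 as the evaluable part of 240.** This implies a loss of 80/240 = 33%. No passage states such a loss for the RCT.

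**The case against.** The strongest reply is that the planned analysis is not a plain change-score test. In the Aim 2 model, "The multiple levels of correlation are captured via the physician-level random effect, ck, and the family-level random effect, bjk"; the model has no arm term at T1, so it behaves like a baseline-adjusted comparison. For Aim 3, "For this Aim, however, the model will include patient-race interaction terms". I computed generalised least squares precision for both models at 160 families and 40 physicians. The assumptions were an SD of change of 12, a physician effect shared by T1 and T2, no stratification covariates, the normal approximation, and T1–T2 correlation r:

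| r | Overall, ICC 0.01 / 0.1 | One race | Interaction |
|---|---|---|---|
| 0.1 | 3.99 / 4.30 | 5.60 / 5.78 | 7.85 / 7.52 |
| 0.3 | 4.32 / 4.54 | 6.08 / 6.21 | 8.55 / 8.31 |
| 0.5 | 4.63 / 4.78 | 6.52 / 6.61 | 9.19 / 9.03 |
| 0.7 | 4.91 / 5.00 | 6.94 / 6.99 | 9.79 / 9.70 |

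This stands in part. The printed overall range is attainable on that model, but the other two ranges need a low r. The protocol states no r and says its calculation uses the difference score, so the model does not explain the printed figures. The result also depends on what the ICC describes. If it applies to the change score, scaling the change-score figures by √((1 + r)/2) gives about 5.2 overall at r = 0.5 and 5.6 at r = 0.7 for ICC 0.1. The protocol does not say which is meant.

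A second objection is that physicians are randomised, so df should be physicians − 2. That is fair, and it makes matters slightly worse: 5.54–6.22 overall at 160 families, and 5.03 with 79.5% power for 5.0 at 240 families, 60 physicians and ICC 0.1. On that basis 240 families do not quite meet even the 5.0.

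A third is that 160 could be the evaluable number. Design & Procedures defines RCT enrolment as meeting all criteria including the NEST threshold, and its list of statuses removes low scorers from enrolment. NEST screen failures are thus already outside the 240, and a 33% loss would have to come from other causes, such as death before T2 or a change of physician. That reading becomes harder to sustain.

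**Conclusion.** The concern holds. On the change-score basis that the protocol names, 160 families detect 5.4–6.1 overall, 7.6–8.0 within one race and about 10–12 for the interaction. Power at the printed differences is 45–63% across all comparisons and formulas, against the stated 80%. The overall result rests only on printed inputs. The one-race result adds an even race mix per physician, and the interaction result adds a choice of formula, none of which reaches the printed range within the protocol's ICC limits. The conflict between 160 and 240 is plain on the page, and 240 does not reproduce the three ranges either. What remains open is whether the planned mixed models would support the overall range. That depends on a T1–T2 correlation and an ICC definition that the documents do not give.

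**What to change.** - State one N and one physician count in the Research Abstract, Design & Procedures, Subject Recruitment and the power paragraph, and say whether N is enrolled or evaluable. If it is evaluable, give the assumed loss.
- Check which N and how many families per physician produced the printed ranges.
- Restate all three detectable differences for that design by one named method. Give the interaction formula, the race split and the degrees of freedom, and say whether the ICC applies to the score or to the change.
- If the change score is kept with 160 families (80/80) and 40 physicians, the figures are 5.4–6.1, 7.6–8.0 and about 10–12 (10.9 by the N/4 reading). If the design is 240, use the 240-family table under the working. The race split matters there: with 100 of 240 families in one race and 40 physicians, that race's figure is 6.84–7.28.
- Alternatively, base the statement on the Aim 2 and Aim 3 models and give the assumed T1–T2 correlation.

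The cost is protocol wording only. On the change-score basis the stated detectable differences become less favourable. No extra patients are needed.

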Aim 2's RCT will be supervised by a single independent central DSMB due to its interventional nature. The DSMB will include professionals with significant experience in clinical trials, mind-body interventions, and biostatistics who are not directly involved in the study, its interpretation, or any study institution. DSMB members will be chosen with the assistance and approval of the NIH. The main responsibilities of the DSMB will be to (a) assess for the presence of potential harms and unintended consequences of the intervention, (b) ensure the validity and integrity of the data, and (c) make recommendations to the NIH about whether the study should be continued without modification, continued with modification, or terminated. The initial DSMB meeting will occur before the initiation of subject enrollment for the purpose of updating members on the study, ensuring agreement on the review process, and establishing the review methodology and procedures. The first DSMB data review will then occur either after the first 10 patients (5 per treatment group) have been enrolled or enrollment has occurred for 3 months, whichever is observed first. Thereafter, the DSMB will review cleaned data pulled from the RedCap database system every six months during enrollment and will prepare a report with any recommendations within the following month. While this is an intensive DSMB engagement schedule, the short enrollment period will demand greater oversight.

The specific study functions and outcomes that the DSMB will review at each meeting include: dropout rate, randomization rate, NEST, PHQ-9, GAD-7, and Post-Traumatic Stress Scale (PTSS) scores. The primary safety measures will be Adverse Events reports and post-intervention PHQ-9 scores. Other items reviewed by the DSMB at each meeting will include: (a) data quality, completeness, and timeliness; (b) performance of the Duke center; (c) adequacy of compliance with goals for recruitment and retention, including women and minorities; (d) protocol adherence; and (e) presence of factors that could adversely affect study outcome or compromise data confidentiality.

During the review process, formal statistical tests for examining the differences in Adverse Event or outcome rates between study groups may be performed under DSMB supervision if requested. However, this is unlikely given the exploratory pilot study design. For differences in study dropout rates, appropriate changes to the protocol will be made by investigator consensus after DSMB member input. Additionally, the DSMB may request a formal statistical assessment if a suspicious increase in PHQ-9 score is observed in either group. If the intervention group is found to have either a statistically significant increase in PHQ-9 score, the DSMB scope of action will include recommendation for cessation of the trial. [name], the biostatistician, will oversee any DSMB statistical requests and interpretations. Any protocol changes, as well as any adverse events, will also be reported to the Institutional Review Boards of all study sites, as well as to the NIH.

Privacy, Data Storage & Confidentiality

• Complete the Privacy and Confidentiality section of the iRIS submission form.

Describe Role of External Personnel:

N/A

NCT03506438

Full Title: Addressing Palliative Care Needs Among Intensive Care Unit Family Members

Document Date: 04/28/2021

Statistical Analysis Plan (Pro00090202)

Statistical Analysis Plan

The goal of the primary hypothesis was to determine the efficacy of the ICUconnect intervention versus usual care on reduction in unmet needs from T1 to T2. Unmet needs were assessed at T1, T2, and T3 with the total NEST score, a continuous, normally distributed measure. Because each family member was surveyed at multiple time points and the same ICU physician saw several patients, outcome variable measurements were not be independent. Therefore hierarchical linear models fit via PROC MIXED in SAS 9.4 (Cary, NC) were used as the primary analytic strategy they appropriately accounted for the multiple types of correlation inherent in our study design. The other continuous, longitudinal outcomes included: PHQ-9, GAD-7, PTSS, and QOC; hierarchical linear models were also used to estimate the treatment effect over time for these outcomes. The binary outcomes of goal concordant care and IPC (dichotomized due to ceiling effects) were analyzed via generalized linear models with a logit link and fit with generalized estimating equations (PROC GENMOD in SAS, 9.4). Finally, treatment group differences in hospital and ICU length of stay were examined with a Wilcoxon test.

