
Aims 2 and 3 of the RCT will be completed simultaneously. The total targeted population for Aims 2 and 3 of the RCT are 240 enrolled patient/family dyads and a maximum of 60 randomized clinicians. To be considered "enrolled" for this study, a patient/family dyad must meet all eligibility criteria and receive a NEST score of > 15.

For aims 2 and 3, the study team will conduct a randomized clustered clinical trial. Randomization occurs at the ICU clinician level versus that of the patient/family level. Clinicians are identified as eligible if they are the current attending on service for the particular ICU. Clinicians are randomized to one of the two arms based on the following:

- 1. Gender (male/female)
- 2. Clinical Experience (<10 years vs > 10 years)
- 3. Discipline (medical vs. surgical)

Consented, enrolled clinicians are expected to complete the following survey(s):

• Baseline Demographics Survey (on the day of consent)

For those clinicians who are randomized to intervention, they will be required to complete the following:

- Review patient/family needs score and survey results within ICUconnect (at the completion of T1 by patient/family dyad)
- Schedule and conduct a family meeting (after T1 completion but before T2 completion)
- Review patient/family needs score and survey results within ICUconnect (at the completion of T2 by patient/family dyad)
- Complete the Clinician Survey via ICUconnect (after Family Meeting and completion of T1 and T2 by patient/family dyad).

Patient/family dyads will be identified at the time of ICU admission and approached for consent based on meeting study inclusion/exclusion criteria (see Selection of Subjects). Each patient/family member, if enrolled into the RCT will be asked to complete an ICUconnect profile and survey (T1). This survey is to be completed within 24 hours of consent to the study. Given that this study's intent is to address unmet needs, eligible participants must receive a NEST score of > 15 (see Study Eligibility Workflow).

- If a participant receives a NEST score of < 15 and they are assigned to a randomized intervention clinician, the participant is considered a screen failure.
- If a participant receives a NEST score of < 15 and is assigned to a randomized control clinician, the
 participant is considered a screen failure for the RCT but is allowed to continue participation within
 the ancillary study.

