Please note that for all scenarios described above, a research introduction may also be completed by the investigators of this study, as they all are routinely physicians on service and dually serve as members of the clinical care team. Research introductions for eligible patient/family dyads provided by investigators will be used as infrequently as possible and only when necessary. This will ensure that coercion to participate in the study is minimized as much as possible.

Eligible clinicians will be introduced to the research study by the investigators of the study. All eligible clinicians will be approached and provided a brief research introduction. If the clinician is interested in participation, he/she will provide verbal or written affirmation to the investigators. The investigators will then inform the study team of the clinician's interest in the study and confirm that it is okay to approach for research. The study team will then contact the clinician, due to their busy schedule, electronically and provide the eConsent (unless otherwise requested by the clinician, in which case paper consent would be utilized).

For the RCT, specifically, the study includes only those participants who self-identify as non-hispanic and either white or black. The purpose of this design is to determine racial disparities experienced among black patients and their families. However, the ancillary study is open to all races and ethnicities and will therefore ensure that the subject selection for this entire project is equitable and all relevant demographic groups have access to study participation.

To meet the statistical power needs for data analysis, the RCT intends to consent approximately 320 patient/family dyads to ensure that 240 patient/family dyads meet all study criteria and are subsequently enrolled. In order to enroll 240 patient/family dyads, 30-60 clinicians will be consented, enrolled and randomized to the study with a relatively equitable split between those clinicians assigned to intervention and those assigned to control.

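### The SAP's GEE for goal concordant care and IPC names no cluster unit, test or small-sample correction; with 30-60 physicians as clusters, an uncorrected Wald test would run modestly above 5%.

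*SAP*

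**What the plan says.** The SAP covers the two outcomes in one sentence. The method is given as "analyzed via generalized linear models with a logit link and fit with generalized estimating equations (PROC GENMOD in SAS, 9.4". The outcomes that it applies to are introduced as "The binary outcomes of goal concordant care and IPC (dichotomized due to ceiling effects". Nothing follows on cluster unit, working correlation, variance estimator, Wald or score test, covariates, or any adjustment for few clusters. The protocol does not fill the gap: its section on Data Analysis & Statistical Considerations describes hierarchical linear models for the RCT comparisons and does not mention GEE.

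The design is clear about where the clustering lies. Under Design & Procedures: "Randomization occurs at the ICU clinician level versus that of the patient/family level". The SAP gives as one reason for its primary approach that "the same ICU physician saw several patients, outcome variable measurements were not be independent". On the number of clusters, Subject Recruitment and Compensation says "30-60 clinicians will be consented, enrolled and randomized to the study", Design & Procedures says "240 enrolled patient/family dyads and a maximum of 60 randomized clinicians", and the power paragraph says "With a sample size of 160 families (4 per each of 40 physicians. 20 per treatment arm".

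NEST and the other continuous outcomes follow a different route: "hierarchical linear models fit via PROC MIXED in SAS 9.4 (Cary, NC) were used as the primary analytic strategy".

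**The concern.** A GEE analysis usually rests on the empirical (sandwich) variance, which is reliable only when there are many independent clusters. With 15-30 physicians per arm it is biased downward. The bias grows when physicians contribute unequal numbers of families and when physician-level covariates are fitted. Unequal numbers are likely here: families enter through whichever attending is on service, and Selection of Subjects sets only a floor of 8 weeks of service per year. Referring the statistic to a normal rather than a t distribution adds to the effect. At stake is whether a borderline result for goal concordant care or IPC can be taken at its printed p-value. The text does not let a reader tell which test produced it.

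**Working it through.** **Plan's own figure.** The documents state no power or error rate for the binary outcomes beyond the two-sided 0.05 level, so there is nothing specific to reproduce. The only cluster-based figure for the RCT is the NEST detectable difference for Hypothesis 2a. With 80 families per arm, SD 12 and DE = 1 + 3 × ICC, (1.96 + 0.84) × 12 × √(2 × DE/80) gives 5.4 (DE 1.03) to 6.1 (DE 1.30), not the stated 4.0 to 5.0. That is a separate matter; only the layout of 40 physicians with 4 families each is used below.

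**Inputs from the documents.** 30, 40 or 60 physicians; 160 families (power paragraph) or 240 (Design & Procedures); two-sided 0.05; ICC 0.01-0.1, which the power paragraph gives for NEST.

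**Assumptions.** The same ICC range for the binary outcomes; event rates of 50-80%; cluster-size CV of 0-0.6. The documents give none of these.

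**Step 1: direction of the bias.** In an arm-only logit GEE with independence working correlation, the robust variance of an arm's log odds is Σ(y_k − n_k p̂)² / [N p̂(1 − p̂)]², summed over that arm's physicians. Each residual is shrunk because p̂ is fitted to the same data, by a factor of about (1 − h_k) in the square, with h_k = n_k/N. With 20 equal clusters per arm, h = 1/20, so the variance is about 5% too small and the SE about 2.5% too small (√0.95 = 0.975). With 15 per arm, h = 1/15 and √(14/15) = 0.966. The normal reference adds to this, and unequal sizes raise h for the larger clusters.

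**Step 2: simulated size under no effect.** Beta-binomial clusters, robust Wald z without correction, nominal 5%:

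| Physicians | Arm only | Three physician-level covariates |
|---|---|---|
| 30 | 5.8-8.2% | 7.2-10.1% |
| 40 | 5.4-7.0% | 6.7-8.4% |
| 60 | 5.2-6.6% | 6.5-7.0% |

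The arm-only column pools independence runs (simulation error about 0.2 points at 20,000 runs) and exchangeable runs (2,500 each, error about 0.5 points). One exchangeable setting at 60 physicians gave 4.9%, which is within that error of the range shown. The covariate column comes from exchangeable runs with 160 families, event rate 75% and CV 0 or 0.5. Three covariates were used because the protocol's NEST model carries three stratification terms.

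**Step 3: the same designs with a correction.**
- Kauermann-Carroll variance with t on (physicians − parameters) df: 4.0-5.7% arm-only, 3.8-6.0% with three covariates.
- Robust score test, arm-only, 160 families, event rate 75%, CV 0.5, 40,000 runs per setting: 5.1-5.4%. It was not run with covariates.

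**Step 4: if the cluster were the family.** Physician correlation would then be left out, and the size is about 2[1 − Φ(1.96/√DE)] with DE = 1 + (m − 1) × ICC. For m = 4:
- ICC 0.01: DE 1.03, 1.96/√1.03 = 1.931, size 5.3%.
- ICC 0.1: DE 1.30, 1.96/√1.30 = 1.719, size 8.6%.

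With 240 families over 40 physicians (m = 6), DE is 1.05-1.50 and the same formula gives 5.6-11.0%.

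**The case against.** The strongest reply is that the SAP is silent rather than wrong. A reader might infer that it commits to plain GEE on physicians with an uncorrected Wald test, and so that its 5% tests run at 6-8%. The documents do not support that. Physician clustering is the natural reading, given the unit of randomization, but it is not stated, and neither is the Wald test. Had a robust score test been used in an arm-only model, the size would have been 5.1-5.4% and there would be little to correct. This part stands, and it is why every figure here is conditional.

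The range also depends on the setting. Values near 8% without covariates need about 30 physicians and unequal clusters. At 40 physicians with equal clusters the size is nearer 5.7%, and at 60 the excess is about 1 point or less in most settings. The event rates, binary ICC and cluster-size CV are assumptions. This stands too.

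The reply does not remove the point. The other plausible cluster unit, the family, also inflates the error. If the GEE carries physician-level covariates, as the NEST model does, the inflation is larger. Only some of the choices that the text leaves open hold the stated level.

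**Conclusion.** The point holds as a specification gap with a modest, conditional consequence. If physicians are the clusters and the robust Wald z is uncorrected, the excess over 5% at the planned 40 physicians is about 0.4-2 points in an arm-only model (5.4-7.0%). Over 30-60 physicians the size is about 5.2-8% arm-only and 6.5-10% with three physician-level covariates. Clustering on family gives about 5.3-8.6% at four families per physician. All of this rests on the assumed event rates, ICC and cluster-size variation set out above.

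A reader might also infer that the trial's main conclusion is at risk. It is not, on this ground: NEST, PHQ-9, GAD-7, PTSS and QOC are analysed by hierarchical linear models. Two non-primary outcomes are affected, and the matter is minor.

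**What to change.** Amend the SAP sentence to state:
- the physician as the GEE cluster;
- the working correlation and the covariates;
- a bias-corrected empirical variance, for example Kauermann-Carroll, with t on (number of physicians − number of physician-level parameters) df. That is physicians − 2 for intercept and arm only, and physicians − 5 with three physician-level covariates.

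A robust score test is an acceptable alternative. Because its size was checked here only without covariates, it should be checked again if covariates are kept.

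The SAP is written in the past tense. If results already exist, state which cluster unit and test produced them, and re-run the two outcomes if the test was uncorrected or clustered on family. The cost is a few lines of code and slightly wider intervals. No change to design, sample size or the primary analysis is needed.
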